8.2.3.1.5. Occurrence status of adverse reactions by inclusion/exclusion in the safety analysis set

For patients with collected case report forms, a listing of adverse reactions in patients excluded from the safety analysis set will be prepared. In addition, the number of patients with adverse events will be tabulated by SOC and PT.

8.2.3.2. Adverse events

8.2.3.2.1. Adverse events by seriousness

The number and proportion of patients with serious adverse events will be tabulated by SOC and PT. Non-serious adverse events will also be tabulated in the same manner. However, the threshold for incidence will be set as necessary, and only events with an incidence at or above the threshold will be tabulated.

8.2.3.3. Exploratory analysis

For each of the factors specified in Section 5.4, the number and proportion of patients with at least one adverse reaction (incidence of any type of adverse reactions) will be tabulated, and for the incidence, the risk ratio among subgroups for each factor will be calculated as described in Section 8.1.3. However, after reconsidering the classification of a category with <10 patients, if calculation of a risk ratio is difficult, the

risk ratio to the category will not be calculated. In addition, unknown data will be excluded from the evaluation of risk ratios.

Serious adverse reactions and serious adverse events will also be analyzed in the same manner as above.

Adverse reactions will be tabulated by SOC and PT for each of the following subgroups:

- Liver impairment [absent, present]
- Renal impairment [absent, present]
- Age [<15 years, ≥15 to <65 years, ≥65 years]
- Pregnancy status [absent, present]
- NYHA functional classification [Class I, II, III, IV]

The onset status of adverse reactions will be evaluated for each product (Vyndaqel or Vynmac) during the treatment period until the first switching to Vynmac for Vyndaqel and during the treatment period after the first switching to Vynmac for Vynmac.

This drug is contraindicated to patients with a history of hypersensitivity to any of its ingredients. Because of limitations in evaluation in this study, no tabulation regarding contraindications will be performed. However, if hypersensitivity to any of its ingredients is reported as an adverse reaction, it will be presented in a listing.

Additional analyses may be performed as necessary. The exploratory analysis will be reported only when results giving important interpretation are obtained.

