#### 8.5. Study size

##### 8.5.1. Sample size

A total of 300 patients will be included in the safety analysis set (SAS).

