##### 8.5.2. Rationale

The number of patients with ATTR-CM in Japan is estimated to be approximately 750. Of these, the proportion of patients who actually received the definitive diagnosis and were prescribed with this drug was estimated to be approximately 40% (approximately 300 patients). As a result, the target sample size was set at 300 subjects from the viewpoint of feasibility. The target sample size of 300 subjects was comparable to the active drug group (264 patients) in the global phase 3 study, and from this point of view, it is considered possible to confirm the safety and effectiveness of the drug to some extent.

If the number of subjects in the SAS is 300, at least 10 subjects with hepatotoxicity can be observed with a probability of approximately 98%, assuming that the true incidence of hepatotoxicity with the lowest incidence based on Studies B3461028 and B3461045 is 5.88% for infections, hypersensitivity reactions, and hepatotoxicity, all of which are important potential risks that can be reviewed.

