##### 2. Method of analysis

- Analysis for safety evaluation

Events possibly related to this drug are considered as adverse drug reactions (ADRs). The number of patients with ADRs and the proportion  $[(\%): \text{number of patients with ADRs} / \text{number of patients included in the SAS}]$  will be calculated.

Based on the above method, important missing information and important potential risks will also be evaluated.

- Analysis for effectiveness evaluation

Time course of changes in the following items from the start of administration of this drug will be recognized.

- NYHA Functional Classification
- Cardiac biomarker values (NT-pro BNP, BNP, troponin I, and troponin T)

In addition, survival time analysis will be performed using survival information obtained up to 30 months after the start of administration.

- Subset analysis

The analysis by variant genotype and NYHA Functional Classification will be also performed for the above safety and effectiveness evaluations.

Also, the onset status of adverse reactions will be evaluated for each product (Vyndaqel or Vynmac) during the treatment period until the first switching to Vynmac for Vyndaqel and during the treatment period after the first switching to Vynmac for Vynmac.

Detailed methodology for summary and statistical analyses of data collected in this study will be documented in the SAP, which will be dated, filed and maintained by the Sponsor. The SAP may modify the plans outlined in the full protocol; any major modifications of primary endpoint definitions or their analyses would be reflected in a full protocol amendment.

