8.2.3.1.4. Safety specifications

For the safety specifications shown in Section 6.1, the number and proportion of patients will be tabulated. The number and proportion of patients with safety specifications will be tabulated by SOC and PT for each action taken and outcome.

In addition, safety specifications will be analyzed, taking into account the difference in exposure period, as described in Section 8.1.4.

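### The SAP does not carry out the protocol's analysis of the important potential risks by TTR type and NYHA class

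*SAP*

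**What the plan says.** Protocol 8.7 (2. Method of analysis) defines the proportion of patients with adverse drug reactions and continues: "Based on the above method, important missing information and important potential risks will also be evaluated". Its subset paragraph then states: "The analysis by variant genotype and NYHA Functional Classification will be also performed for the above safety and effectiveness evaluations". The important potential risks are listed in Protocol 7.1 and SAP 6.1. Protocol 8.5.2 treats three of them as open to review in this survey: infections, hypersensitivity reactions and hepatotoxicity. Protocol 7.1 also names use in patients with variants as important missing information.

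SAP 8.2.3.1.4 reads: "For the safety specifications shown in Section 6.1, the number and proportion of patients will be tabulated". It adds tables by SOC and PT for action taken and outcome, and an analysis that allows for exposure. It names no subgroup factor.

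SAP 8.2.3.3 takes every factor of Section 5.4 and says that "the number and proportion of patients with at least one adverse reaction (incidence of any type of adverse reactions) will be tabulated", with risk ratios between subgroups. Serious adverse reactions and serious adverse events are handled in the same way. It then orders SOC/PT tables of adverse reactions for liver impairment, renal impairment, age, pregnancy status and NYHA I–IV. TTR type is not in that list. SAP 9 provides a listing of variant patients with adverse reactions and a listing of reactions by safety specification.

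**The concern.** The survey's safety questions concern particular risks and particular patients. The protocol joins the two by asking for the safety evaluation, potential risks included, by variant genotype and NYHA class. In the SAP they stay apart: the risks are analysed without subgroups, and the subgroups are compared by risk ratio only on pooled outcomes.

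A ratio for any adverse reaction mixes the risk of interest with every unrelated reaction. If the unrelated reactions are similar in both groups, they pull a real difference towards 1. SAP 8.2.3.3 also reports exploratory results only when they are judged important to interpretation, so a diluted ratio may not be reported at all. The gap is widest for TTR type, where no event-level table sets variant against wild-type patients.

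**Working it through.** **1. Protocol against SAP.**

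| Output | TTR type | NYHA class |
|---|---|---|
| Important potential risks (Protocol 8.7) | called for | called for |
| Important potential risks (SAP 8.2.3.1.4) | no | no |
| Any reaction, serious reactions, serious events, with risk ratio (SAP 8.2.3.3) | yes | yes |
| Adverse reactions by SOC and PT (SAP 8.2.3.3) | no | yes, I–IV, no risk ratio specified |
| Patient listing for the subgroup (SAP 9) | variants only | no |

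No section of the SAP crosses a defined potential risk with a subgroup factor.

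**2. The plan's own figure.** Protocol 8.5.2 states that, with 300 patients and a true incidence of 5.88%, "at least 10 subjects with hepatotoxicity can be observed with a probability of approximately 98" per cent. The exact binomial P(X ≥ 10) for n = 300 and p = 0.0588 is 0.984, so the figure reproduces. Expected cases are 300 × 0.0588 = 17.6.

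**3. Size of the dilution (illustration).** From the documents: N = 300, overall incidence p = 5.88%, and the Wald interval for the risk ratio (SAP 8.1.3). Assumed, because the documents do not give them:
- variant share v of 10–30%;
- a true risk-specific ratio RR of 3 or 2;
- other reactions at rate q of 10–40%, equal in both groups and independent of the risk.

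The 5.88% is treated as a rate of adverse reactions; the protocol does not say whether it counts reactions or events of any cause.

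Formulas:
- risk in wild-type: p0 = p / (v × RR + 1 − v); in variants: p1 = RR × p0
- any reaction in each group: 1 − (1 − p_group)(1 − q)
- standard error of the log ratio: √(1/a − 1/n1 + 1/b − 1/n0), where a and b are the expected cases in the two groups

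For v = 20% (60 against 240 patients) and RR = 3: p0 = 0.0588 / 1.4 = 4.2% and p1 = 12.6%. Expected cases are 60 × 0.126 = 7.6 and 240 × 0.042 = 10.1. The standard error is 0.459, so the risk-specific ratio is 3.0 (95% CI 1.22 to 7.38).

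| q | Any reaction, variant | Any reaction, wild-type | Ratio (95% CI) |
|---|---|---|---|
| 10% | 21.3% | 13.8% | 1.55 (0.87 to 2.77) |
| 20% | 30.1% | 23.4% | 1.29 (0.82 to 2.02) |
| 30% | 38.8% | 32.9% | 1.18 (0.82 to 1.70) |
| 40% | 47.6% | 42.5% | 1.12 (0.83 to 1.52) |

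Over v = 10–30% and q = 10–40%, a true ratio of 3 appears as 1.61 down to 1.10, and a true ratio of 2 as 1.32 down to 1.06. With a true ratio of 2 and v = 20%, the risk-specific interval itself includes 1 (0.77 to 5.16).

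**The case against.** A reader might infer that the SAP looks at subgroups only through pooled outcomes. It does not: the SOC/PT tables by NYHA I–IV and by liver impairment show component events, and a SOC row counts each patient once. If a risk lay within one SOC, much of it would be visible there. This stands, and it makes the gap partial for NYHA class. It does not close it. The risk definitions are in a separate document and may span several terms or SOCs, PT rows cannot be summed to patients, and no risk ratio is specified for these tables.

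A reader might also infer that the protocol promises these risks by liver impairment. Protocol 8.7 names only variant genotype and NYHA class. Severe hepatic impairment enters as important missing information, which the SAP addresses through a subgroup factor and a listing.

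Nor do the documents support saying that the survey would declare no difference. SAP 4.1 sets no significance level, and no rule turns an interval that includes 1 into a conclusion.

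Finally, Protocol 8.7 lets the SAP modify its plans, the survey is not confirmatory, and SAP 8.2.3.3 permits additional analyses. All true. But the SAP does not say that it is dropping this analysis, and permission for further analyses commits to none. The listings give case details for what will be few cases, but no denominators.

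**Conclusion.** The concern holds in a limited form. The SAP omits a descriptive analysis that a plain reading of Protocol 8.7 calls for: the important potential risks by TTR type and NYHA class. For TTR type there are only pooled outcomes and a listing; for NYHA class the SOC/PT tables help in part. Under the stated assumptions the pooled comparison shrinks a true ratio of 3 to about 1.1–1.6. The direction of that result rests on other reactions being similar in both groups; its size rests on the assumed variant share and reaction rate. No figure stated in the documents is wrong. About 18 expected hepatotoxicity cases will not support firm subgroup conclusions, so what is lost is a relevant description, not a powered test.

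**What to change.** In SAP 8.2.3.3, add a tabulation of hepatotoxicity, hypersensitivity reactions and infection, each as one grouped event under the definitions already used for Section 8.2.3.1.4. Do this by TTR type [wild-type, variant] and NYHA class [I/II, III/IV] only. Give n/N with the exact 95% CI of Section 8.1.3, and a risk ratio where counts allow. Add TTR type to the list of subgroups tabulated by SOC and PT. Liver impairment may be added as an option; Protocol 8.7 does not require it.

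The cost is 3 risks × 2 factors = 6 short tables and one further SOC/PT table, from data already collected and grouped. Naming the two factors matters: applying the three risks to all 13 factors of Section 5.4 would give 39 analyses. Cells will be small and intervals wide, and the report should present the tables as descriptive.

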#### **8.2.6. Observation period**

[figure not shown]
30 months (Week 130) from the start of administration (Day 1)

However, for patients who discontinued this drug during the observation period, the observation period will be until the first visit after the date of discontinuation.

[figure not shown]
In this study, information will be collected using a booklet type CRF. Information during the following periods will be entered in each booklet.

If the patient is transferred to another hospital or department (hereinafter referred to as hospital transfer) during the observation period, the patient will be newly registered even at the transferred site and the CRF will be completed. If the patient is transferred to another hospital, the patient registration number of the original site will be conveyed to the transferred site. Although the patient will be given a new patient registration number at the transferred site at the time of registration, he or she will be determined to be a transferred patient by reporting the patient registration number of the original site and his/her data will be handled as the same patient. If the time point of 30 months after the start date of initial administration can be identified for the transferred patient, the observation period at the transferred site may be reset so that the total observation period of the patient in this study will become 30 months.

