## 10.2. Reporting period

For each patient, the safety event reporting period begins at the time of the patient's first dose of this drug, and lasts through the end of the observation period of the study, which must include at least 28 calendar days following the last administration of a drug under study; a report must be submitted to Pfizer Safety (or its designated representative) for any of

PFIZER CONFIDENTIAL

CT24-WI-JPN-GPSP01-RF09 7.0 Non-Interventional Study Protocol Template for Secondary Data Collection

Study 15-Sep-2022

Page 28 of 39

the types of safety events listed in the table above occurring during this period. If a patient was administered a drug under study on the last day of the observation period, then the reporting period should be extended for 28 calendar days following the end of observation. If the investigator becomes aware of a SAE occurring at any time after completion of the study and s/he considers the SAE to be related to this drug, the SAE also must be reported to Pfizer Safety.

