2.1. Study Design

Investigation period: March 2019 to September 2023 (From the start date of observation for the first subject to the end date of observation period for the last subject)

Registration period: March 2019 to March 2021 (From the start date of treatment for the first subject to the start date of observation period for the last subject)

Study patients: This study will be conducted with all patients surveillance system that all patients will be registered until data are collected on a target number of patients.

Target sample size: The number of patients with ATTR-CM in Japan is estimated to be approximately 750. Of these, the proportion of patients who actually received the definitive diagnosis and were prescribed with this drug was estimated to be approximately 40% (approximately 300 patients). As a result, the target sample size was set at 300 subjects from the viewpoint of feasibility. (300 patients to be evaluated for the safety of this drug)

Observation period: 30 months (Week 130) from the start of administration (Day 1). However, for patients who discontinued this drug during the observation period, the observation period will be until the first visit after the date of discontinuation.

Handling of patients transferred to another hospital or department: For the proper use of this drug, requirements for patients, institutions, and physicians have been specified by the Japanese Circulation Society¹, and it is necessary to meet all of these requirements to introduce this drug. However, since continued prescription at another institution is allowed in consideration of convenience, patients who have already started to receive this drug may be transferred to another hospital or department. If the patient is transferred to another hospital or department (hereinafter referred to as hospital transfer) during the observation period, the patient will be newly registered even at the transferred site and the CRF will be completed. If the patient is transferred to another hospital, the patient registration number of the original

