site will be conveyed to the transferred site. Although the patient will be given a new patient registration number at the transferred site at the time of registration, he or she will be determined to be a transferred patient by reporting the patient registration number of the original site and his/her data will be handled as the same patient. However, registration is not necessary when the date of starting the treatment at the transferred site is on or after 01 April 2021. If the time point of 30 months after the start date of initial administration can be identified for the transferred patient, the observation period at the transferred site may be reset so that the total observation period of the patient in this study will become 30 months.

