8.1.3. Analysis of binary data

The frequency and its proportion will be calculated. When the confidence interval of the proportion is calculated, the two-sided 95% confidence interval (exact method) will be calculated.

When the proportion is compared between subgroups, the risk ratio and its 95% confidence interval (Wald method) will be calculated.

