8.1.6. Analysis based on the person-years method

The incidence rate per exposure period will be calculated using the following formula:

$$\text{Incidence rate (per 100 person-years)} = 100 * y / PT$$

y: Number of patients with event

PT: Total exposure period (years)

Where the exposure period is the period from the first date of administration to the date of last observation in this study for patients with no event and the period from the first date of administration to the first date

of confirmation of the event in this study for patients with an event. The 95% confidence interval will be calculated using the following formula:

$$\left[\frac{100}{PT} \cdot \frac{1}{2} \chi^2_{2y} \left(\frac{\alpha}{2} \right), \frac{100}{PT} \cdot \frac{1}{2} \chi^2_{2(y+1)} \left(1 - \frac{\alpha}{2} \right) \right]$$

y: Number of events

$\chi^2_{2y}(\alpha/2)$: $\alpha/2$ percent point of the chi-square distribution with $2y$ degrees of freedom

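### Subgroup risk ratios for adverse reactions and serious events use crude proportions despite unequal follow-up, so they are not comparable at equal exposure; add person-years rates beside them

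*SAP*

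**What the plan says.** SAP 8.2.3.3 takes each Section 5.4 factor, counts the patients with at least one adverse reaction, and states that "the risk ratio among subgroups for each factor will be calculated as described in Section 8.1.3". Section 8.1.3 has no time term: "When the proportion is compared between subgroups, the risk ratio and its 95% confidence interval (Wald method) will be calculated". The method extends beyond reactions: "Serious adverse reactions and serious adverse events will also be analyzed in the same manner as above".

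Follow-up is unequal by design. The plan is 30 months from first administration, but Protocol 8.2.6 says that "for patients who discontinued this drug during the observation period, the observation period will be until the first visit after the date of discontinuation". Protocol 10.2 sets a safety reporting period "which must include at least 28 calendar days following the last administration of a drug under study", a short tail against 30 months. Transfers may also shorten follow-up: SAP 2.1 says that "registration is not necessary when the date of starting the treatment at the transferred site is on or after 01 April 2021".

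The SAP deals with exposure in other places:
- Section 8.1.6 defines a person-years method ("The incidence rate per exposure period will be calculated using the following formula"), but no analysis section cites it by number.
- Section 8.2.3.1.4 asks for an analysis of the safety specifications that allows for differing exposure, and points to 8.1.4 (Kaplan-Meier).
- Section 8.2.3.1.3 uses period-specific denominators in the time-to-onset table.

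Neither of these two analyses is specified by subgroup.

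**The concern.** A patient observed for 3 months without an event weighs as much in the denominator as one observed for 30 months without an event. The ratio therefore mixes how often events occur with how long each subgroup was watched. Several Section 5.4 factors (NYHA class, liver impairment, renal impairment) could plausibly be linked to time on drug.

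The study's objective is long-term safety. The two starred factors in Section 5.4, severity of liver impairment and TTR variant, are how the SAP evaluates the important missing information. A ratio near 1 there could be read as reassurance when part of it reflects shorter observation. Protocol 8.9 lists limitations but not unequal follow-up.

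**Working it through.** **Plan figures.** The documents give no event or exit rate by subgroup, so there is no plan figure for this comparison to reproduce. The one probability in Protocol 8.5.2 (at least 10 hepatotoxicity cases among 300 patients at 5.88%) comes to 0.984 by the exact binomial, which agrees with the stated 98%. It is not in dispute.

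**Inputs.** From the documents: T = 30 months; follow-up ends on leaving; non-events remain in the denominator. Assumed: constant hazards, a 30-month reaction risk of 20% under full follow-up, and exits unrelated to reactions.

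**Formulas.** Event hazard h = −ln(1 − 0.20)/30 = 0.00744 per month. Exit hazard c = −ln(1 − exit proportion)/30. Expected crude proportion = h/(h + c) × [1 − exp(−30(h + c))].

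**Equal event rates in both groups:**

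| Leaving, reference v comparison | Crude proportions | Crude ratio |
|---|---|---|
| 20% v 20% | 0.180 v 0.180 | 1.00 |
| 20% v 40% | 0.180 v 0.158 | 0.88 |
| 20% v 50% | 0.180 v 0.146 | 0.81 |
| 30% v 60% | 0.169 v 0.133 | 0.79 |

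With a reaction risk of 10% or 30% these ratios change by less than 0.01.

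**A real excess, 20% v 50% leaving.** Like must be compared with like, so the benchmark is the risk ratio under full follow-up.
- Hazard ratio 1.25: full-follow-up risk 1 − 0.8^1.25 = 0.243, ratio 0.243/0.200 = 1.22. Crude ratio 0.178/0.180 = 0.99.
- Hazard ratio 1.5: full-follow-up risk 1 − 0.8^1.5 = 0.284, ratio 1.42. Crude ratio 0.209/0.180 = 1.16.

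**Person-years rate, same model, equal hazards, 20% v 50% leaving.** Mean time at risk is 24.20 v 19.64 months. The rates are 0.1800/24.20 = 0.00744 and 0.1461/19.64 = 0.00744, so the rate ratio is 1.00.

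**If reactions cluster early.** Keep the 20% risk and equal hazards, but put 70% of the cumulative hazard in the first 6 months. With 20% v 50% leaving:
- Crude ratio: 0.172/0.190 = 0.91.
- Rate ratio: (0.1724/18.51)/(0.1901/22.85) = 1.12.

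The two measures then err in opposite directions.

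**Serious adverse events, with death counted as an event.** Assume non-fatal events in 30% of both groups and death in 10% v 30%. Full-follow-up risks are 1 − 0.7 × 0.9 = 0.37 and 1 − 0.7 × 0.7 = 0.51, ratio 1.38.
- No other exits, or 10% in each group: crude ratio 1.38.
- Other exits 10% v 30%: crude ratio 0.438/0.353 = 1.24.

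**The case against.** A reader might infer that the plan does understate risk in the sicker subgroups. The documents do not support that. They give no exit rates by subgroup, and with equal exit there is no material bias. Only a conditional statement stands.

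A reader might also infer that everyone who leaves early counts as event-free. Adverse events are a listed reason for discontinuation (Protocol 8.3.6), and a patient who stops because of a reaction is already in the numerator. Take a 15% reaction risk and 15% v 50% leaving. If none, a quarter or half of the exits are themselves reactions, the crude ratio is 0.79, 1.30 or 1.64, against full-follow-up ratios of 1.00, 1.55 and 1.84. The shortfall falls from 21% to 16% to 11%. It shrinks but does not vanish.

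For serious adverse events, the argument from death fails. Death is a seriousness criterion (Protocol 10.4.2), so dying adds to the numerator. For adverse reactions, death is a competing event: the crude proportion remains a valid on-study incidence, though not a comparison at equal exposure.

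The consequences are also limited. SAP Section 4 makes the analyses exploratory with no significance level. For an assumed split of 200 v 100 patients at 20% risk, the Wald limits lie a factor of exp(1.96 × √(0.8/40 + 0.8/20)) = 1.6 either side, wider than a 12–21% shift. Ratios may be dropped for categories with fewer than 10 patients, and Section 9 lists reactions individually for severe liver impairment and for variants.

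All of this narrows the point. It does not supply an exposure-adjusted comparison by subgroup, which the SAP lacks.

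**Conclusion.** The point holds in conditional form. The Section 5.4 risk ratios are not comparable at equal exposure, and they may understate risk in any subgroup that is followed for less time, including the starred factors. Under constant hazards, 20% risk and exits unrelated to reactions, the crude ratio falls 12% to 21% below 1 at equal event rates for the exit patterns shown. With 20% v 50% leaving, full-follow-up risk ratios of 1.22 and 1.42 appear as 0.99 and 1.16. The exit rates are assumptions throughout. For serious adverse events, only unequal exit without an event causes understatement.

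It would also go too far to conclude that the rate ratio should take over as the basis of interpretation. It relies on a roughly constant rate, and in the early-clustering example it errs by about as much as the crude ratio, upwards. The case is for showing both. This is a cheap improvement to an exploratory analysis, not a flaw that undermines the study.

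**What to change.** In SAP 8.2.3.3, for each Section 5.4 category and each of the three outcomes, add:
- total follow-up time;
- the incidence rate per 100 person-years by Section 8.1.6, counting the first event;
- the rate ratio to the same reference category with its 95% CI. Section 8.1.6 gives an interval for a single rate only, so name the method for the ratio, for example a Wald interval on the log scale with standard error √(1/y₁ + 1/y₀), where y₁ and y₀ are the numbers of patients with an event.

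Report these beside the crude risk ratio and read the two together. State that time at risk ends at the first event, death or last observation. Say also how events recorded after last observation are treated, because Section 8.2.3 counts all events collected after the start of administration. Show the columns for every factor, since 8.2.3.3 otherwise reports exploratory results selectively. Where early clustering is a concern, add cumulative incidence by subgroup with death as a competing event. If Section 8.1.6 was the intended reference in 8.2.3.1.4, correct that too.

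The cost is SAP wording and a few table columns. No new data are needed: the protocol already collects the first day of treatment, event dates, the end date of observation and the date of death. The downside is the constant-rate assumption, which is why the rate ratio should not stand alone.
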